5.5 Multiple Comparisons

Due to the exploratory nature of this study, no corrections for multiple comparisons are planned for this study.

5.6 Data Derivations and Transformations

See section 5.3.

6. STUDY PARTICIPANTS

6.1 Demographic Characteristics

Descriptive statistics will be used to summarize the demographic characteristics (age, gender, race and ethnicity) for the safety and longitudinal safety population. These will be displayed by cohort (1a, 1b and 2) and by the individual sub-cohorts described in Section 5.2.

Demographics characteristics will be tabulated separately for values collected at the start of the Parent Study and values collected at the start of Study ARCT-021-02

6.2 Baseline Characteristics

Baseline characteristics including weight, height, BMI, and vital signs will be listed and summarized using descriptive statistics for the safety population.

6.3 Medical History

All medical conditions and surgical procedures will be classified by system organ class (SOC) and preferred term (PT) using the Medical Dictionary for Regulatory Activities (MedDRA version 23.0). The number and percent of participants with each medical condition and surgical procedure will be presented for each SOC and PT for the safety population. Any adverse events occurring prior to first

injection of Study vaccine will be captured as medical history.

For participants that received placebo in the Parent Study, SAEs, CESIs, NOCD and MAAEs that occurred since completion of the Parent Study and screening for this study will be recorded and they will be reported as medical history.

6.4 Prior and Concomitant Medications

Concomitant medications including vaccines will be coded using World Health Organization (WHO) drug (version WhoDrug B3G March 2020) classifications. The number and percent of safety participants using concomitant medications will be tabulated by Anatomical, Therapeutic, and Chemical (ATC) class and by preferred name for the safety population.

A Medication is considered Prior if it was prescribed prior to Day 1 regardless of whether it continued to be administered after vaccination. For participants in Cohort 1a, medication received prior to Day 1 of ARCT-021-02 will be considered Prior. For participants in Cohorts 1b and 2, medication received prior to Day 1 in the Parent Study will be considered Prior.

Only medications which have been taken since end of parent study will be reported.

7. IMMUNOGENICITY ANALYSIS

Humoral immune responses (immunogenicity) will be assessed in the Immunogenicity Population. Cellular responses are not being evaluated at this interim analysis.

7.1 Primary Immunogenicity Endpoint and Analysis

Immunogenicity is not a primary endpoint defined for this study.

7.2 Secondary Immunogenicity Endpoints and Analyses

As per scheduled assessment, Cohort 1 will be reported at Study Day 29, Study Day 57, Study Day 169 and Study Day 365/Early termination, however only immunogenicity data up to ARCT-021-02 Day 57 will be available at the time of this interim. Cohort 2 will be reported at Study Day 29 (6 months FU), Study Day 197(12 Months FU) and Study Day 281 (15 Month FU)/Early Termination, however only immunogenicity data up to ARCT-021-02 Day 29 will be available at the time of this interim.

1. Mean and geometric mean titer or concentration (GMT, GMC) and the geometric mean fold rise (GMFR) in SARS-CoV- 2 neutralising antibody titer and IgG antibodies against the full-length SARS-CoV-2 recombinant spike protein antigen, RBD and N-antigen at multiple time points in each cohort.

Assessment of the long-term neutralising and anti-spike glycoprotein responses, including seroconversion rates, following vaccination with ARCT-021 is the secondary objective of the study. The study endpoint for these analyses include:

Assays:

- Neutralising antibody responses: pseudovirus neutralization test

- Binding antibody responses: Total IgG against the full-length SARS-CoV-2 recombinant spike protein, RBD and N-antigen will be assessed using a Meso-Scale Discovery (MSD) multiplex technology.

Endpoints at this interim:

- Cohort 1: Neutralising and binding antibody responses at Day 1, Day 29 (1 month after last dose of ARCT-021), Day 57 (2 months after last dose of ARCT-021)
- Cohort 2: Neutralising and binding antibody responses at ARCT-021-02 Day 29 (6 months after last dose of ARCT-021), which is Day 176 for Cohort 2 (A to D2) and Day 204 for Cohort 2 (E to H)

Descriptive statistics, by assessment time point, will be used to describe all immunogenicity results.

Mean and geometric mean titer (GMT) and geometric mean fold rise (GMFR) will be calculated for each cohort/sub-cohort (Section 5.2) in the Immunogenicity analysis population. The %GCV, median, standard deviation, minimum, and maximum values will also be displayed.

The GMT will be calculated as:

$$\text{GMT} = \text{anti-log}_{10} (\text{mean} [\log_{10} Y_i])$$

The GMFR will be calculated as:

$$\text{GMFR} = \text{anti-log}_{10} (\text{mean} [\log_{10} Y_i / B_i])$$

where Y_i is the post dose assay result for participant i ; and B_i is the baseline assay result for participant i . The exact 95% CIs will be provided for both GMT and GMFR.

2. Proportion of ARCT-021-naïve participants seroconverting for neutralizing antibodies and IgG antibodies against the full-length SARS-CoV-2 recombinant spike protein antigen and spike protein RBD will be assessed at the above mentioned time points. Seroconversion will be defined as a 4-fold increase in antibody titer/concentration from baseline. An additional analysis at a threshold of 2-fold increase from baseline will also be performed.

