***Subjects that terminate early should complete all procedures for Study Day 365**

- 1 Full physical exam to be given at Day 1 and Day 365/Early Termination; abbreviated physical exam (assessment of vitals, heart, lungs, lymphatic, abdomen and symptom directed examination, if any symptoms) to be given during treatment and follow-up period to assess changes from screening. Injection site to be inspected at all visits after injection until resolution of local reactogenicity event(s).
- 2 BP, HR, RR, temp
- 3 Women who are not surgically sterile or post-menopausal. Dipstick acceptable
- 4 Dipstick test per local procedures. If abnormal send sample to laboratory for microscopy.
- 5 Stored at -70 °C for follow up immunological assessments or exploration of laboratory findings and/or adverse events
- 6 Can be done at the site using established methods, e.g., a breathalyzer or urine test.

- 7 Symptom diary to be reviewed on Day 8. If subject has any unresolved local or systemic reactogenic events then they should be instructed to continue to complete the symptom diary for a further week and the symptom diary should be reviewed again at Day 15. This review includes specifically asking about injection site and systemic (fever, fatigue, headache, chills, nausea, vomiting, diarrhoea, new or worsened myalgia, and new or worsened arthralgia) events. If not being completed for the second week after injection, then the symptom diary will be collected on Day 8; otherwise symptom diary to be collected on Day 15.
- 8 Only SAE, CESI, NOCD and MAAE will continue to be recorded after Day 29.
- 9 At each visit, subjects will be questioned about symptoms of COVID-19 and exposure to confirmed COVID-19 or confirmed SARS-CoV-2 infection cases amongst household contacts, friends, work contacts and other contacts.
- 10 Subjects that terminate from the study before completion will be told to inform the study site staff if they develop symptoms compatible with COVID-19 (Section 6.2.4), or a diagnosis of SARS-CoV-2 infection or COVID-19 for one year after vaccination so that they can be adequately followed up.

Time (time is in reference to Study Drug administration):

a Pre-dose

If not specifically labeled, "X" means anytime

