1. INTRODUCTION

This is a Statistical Analysis Plan for an Interim Analysis of Arcturus Therapeutics, Inc.'s study protocol ARCT-021-02 titled "A Phase 2a, Open Label Extension Study to Assess the Safety and Long-Term Immunogenicity of ARCT-021". See the protocol for additional details.

This SAP is based on protocol version 2.0 and provides details of the statistical analyses specified in the study protocol.

This study will be conducted in compliance with the study protocol and analyses will be conducted in compliance with ICH guideline E9 (Statistical Principles for Clinical Trials 1998), as applicable.

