5.3.1 Baseline

For Safety Analysis, the following conventions will be applied for the definition of baseline:

For the Safety Population baseline will be the last value prior to first administration of ARCT-021 in Study ARCT-021-02.

For the Longitudinal Safety Population baseline will be the last value prior to first administration of ARCT-021 in either the ARCT-021-01 or ARCT-021-02 study (whichever study represented the first ARCT-021 vaccination)

For the Immunogenicity Analysis, Immunogenicity baseline will be defined as:

- Cohort 1a and 1b: Last value prior to or on Day 1 of ARCT-021-02
- Cohorts 2 (A to D2) and 2 (E to H): Last value prior to or on Day 1 of ARCT-021-01

For assessments collected during the screening period as well as on Day 1, the Day 1 value will be used as baseline. If more than one assessment exists within a single visit window, the value closest to the protocol study visit will be used for summary and analysis purposes. If more than one equidistant to the protocol study visit assessments exists, then earliest of these values will be used for summary and analysis purposes. Data from all assessments will be listed.

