5.3.2 Study Day in Study ARCT-021-02

For Adverse events, Study day will be determined based on actual number of days since study Day 1. Study Day 1 will be identified from the CRF. For Cohort 1, it will be the day of vaccination. Study day for any given date will be:

- Given Date – Study Day 1 + 1 for dates on or after date of Study Day 1.
- Given Date – Study Day 1 for dates before date of Study Day 1.

For all immunogenicity data, the Study Day will be based on the nominal study day as captured in the CRF. For participants that received their first dose of ARCT-021 in the Parent study, nominal day since Day 1 in the Parent Study will also be displayed, as follows:

- For cohorts 1b (A to D2) and 2 (A to D2) Day 1 in Study ARCT-021-02 = Day 147 after Day 1 in the Parent Study, calculated as follows:
 - The time enrolled in the Parent Study is 57 days and the time between Parent Study and Day 1 in Study ARCT-021-02 is nominally 90 Days. Therefore, Day 1 in Study ARCT-021-02 is $57 + 90 = 147$ days after Day 1 in the Parent Study
- For cohorts 2 (E to H) Day 1 in Study ARCT-021-02 = Day 175 after Day 1 in the Parent Study, calculated as follows:
 - The time enrolled in the Parent Study is 85 days and the time between Parent Study and Day 1 in Study ARCT-021-02 is nominally 90 Days. Therefore, Day 1 in Study ARCT-021-02 is $85 + 90 = 175$ days after Day 1 in the Parent Study

Based on the above, in the Immunogenicity tables the visit name (when they are shown) will be displayed showing the nominal day from parent study within parenthesis. The nominal days will depend on the cohort and they will be as follows:

Table 3: Label for reporting Visit Days in safety and immunogenicity when needed.

Visit name in Protocol	Cohort			
	1a	1b	2 (A-D2)	2(E-H)
Day 1	Day 1	Day 1 (147)	Day 1 (147)	Day 1 (175)
Day 29	Day 29	Day 29 (175)	Day 29 (175)	Day 29 (203)
Day 43	Day 43	Day 43 (189)	Day 43 (189)	Day 43 (217)
Day 57	Day 57	Day 57 (203)	Day 57 (203)	Day 57 (231)
Day 85	Day 85	Day 85 (231)	Day 85 (231)	Day 85 (259)

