Assessment after Screening Period

Participants Not receiving ARCT-021 in This Study.

Study Week/Day	Observation Period (40 Weeks)				
	W1 D1	W5 D29	W13 D85	W29 D197	W41 D281/or Early Term*
Visit Window (Days)	0	± 7	± 7	± 14	± 14
Physical Exam ¹	X		X	X	X
Vital Sign ²	X		X	X	X
Archived plasma sample ³	X	X	X	X	X
Archived serum sample ³	X	X	X	X	X
Archived PBMC sample ³	X	X	X	X	X
Immunogenicity		X		X	X
T-cell response		X		X	X
SAE, CESI, NOCD and MAAE ⁴	X	X	X	X	X
SARS-CoV-2 questioning ⁵	X	X	X	X	X
Counselling about long term follow-up for SARS-CoV-2 infection ⁶					X

* Participants that terminate early should complete all procedures for Study Day 281

1 Abbreviated physical exam (assessment of vitals, heart, lungs, lymphatic, abdomen and symptoms directed examination, if any symptom) to be given during observation period to assess changes from screening.

2 BP, HR RR, temp.

3 Stored at -70°C for follow up immunological assessment or exploration of laboratory findings and/or adverse events.

4 SAE, CESI, NOCD and MAAE will be recorded.

5 At each visit participants will be questioned about symptoms of COVID-19 and exposure to confirmed COVID-19 or confirmed SARS-COV-2 infection cases amongst household contacts, friends, work contacts and other contacts.

6 Participants that terminate from the study before completion will be told to inform the study site staff if they develop symptoms compatible with COVID-19 (Section 6.2.4), or a diagnosis of SARS-CoV-2 infection or COVID-19 for one year after vaccination so that they can be adequately followed up.

Participants Receiving a Single Injection of ARCT-021 in This Study.

Study Week/Day	Study vaccine Administration	Post-Treatment Period (52 Weeks)						
		W2 D8	W3 D15	W5 D29	W9 D57	W25 D169	W37 D253	W53 D365/ Early Term*
Visit Window (Days)	0	±1	±1	0	±7	±14	±14	±14
Physical Exam ¹	X ^a	X	X	X	X	X	X	X
Vital Sign ²	X ^a	X	X	X	X	X	X	X
Pregnancy Test ³	X ^a							
Chemistry Panel	X ^a	X	X	X				
Hematology	X ^a	X	X	X				
Coagulation	X ^a							
HbA1c	X ^a							
Urinalysis ⁴	X ^a	X		X				
Archived plasma sample ⁵	X ^a			X	X	X	X	X
Archived serum sample ⁵	X ^a			X	X	X	X	X
Archived PBMC sample ⁵	X ^a		X	X	X	X	X	X
Immunogenicity	X ^a			X	X	X		X
T-cell responses	X ^a		X	X		X		X
Drug/Alcohol Screen ⁶	X ^a							
Study vaccine Administration	X							
Review of symptom Diary ⁷		X	X					
Unsolicited AE	X	X	X	X				
SAE, CESI, NOCD and MAAE ⁸	X	X	X	X	X	X	X	X
Concomitant Medications and Procedures	X	X	X	X				

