SARS-CoV-2 questioning ⁹	X	X	X	X	X	X	X	X
Counselling about long term follow-up for SARS-CoV-2 infection ¹⁰								X

* Participants that terminate early should complete all procedures for Study Day 365.

- 1 Full Physical Exam to be given at Day1 and Day 365/Early Termination; abbreviated physical exam (assessment of vitals, heart, lungs, lymphatic, abdomen and symptoms directed examination, if any symptom) to be given during treatment and follow-up period to assess changes from screening. Injection site to be inspected at all visits after injection until resolution of local reactogenicity event (s).
- 2 BP, HR RR, temp.
- 3 Women who are not surgically sterile or post-menstrual. Dipstick acceptable.
- 4 Dipstick test per local procedures. If abnormal, send sample to laboratory for microscopy.
- 5 Stored at -70°C for follow-up immunological assessment or exploration of laboratory findings and/or adverse events.
- 6 Can be done at the site using established methods, e.g. a breathalyzer or urine test.

- 7 Symptom diary to be reviewed on Day 8. If participant has any unresolved local or systemic reactogenic events, then they should be instructed to continue to complete the symptom diary for a further week and the symptom diary should be reviewed again at Day 15. This review includes specifically asking about injection site and systemic (fever, fatigue, headache, chills, nausea, vomiting, diarrhoea, new or worsened myalgia, and new or worsened arthralgia) events. If not being completed for the second week after injection, then the symptom diary will be collected on Day 8; otherwise, symptom diary to be collected on Day 15.
- 8 Only SAE, CESI, NOCD and MAAE will continue to be recorded after Day 29..
- 9 At each visit participants will be questioned about symptoms of COVID-19 and exposure to confirmed COVID-19 or confirmed SARS-COV-2 infection cases amongst household contacts, friends, work contacts and other contacts.
- 10 Participants that terminate from the study before completion will be told to inform the study site staff if they develop symptoms compatible with COVID-19 (Section 6.2.4), or a diagnosis of SARS-CoV-2 infection or COVID-19 for one year after vaccination so that they can be adequately followed up.

Time (time is in reference to Study vaccine administration):

a Pre-dose

If not specifically labeled, “X” means anytime

10.2 Appendix B: List of Laboratory Analytes.

List of Laboratory Analytes for Which Data Available at this Interim

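### SAP 7.2 merges early termination with the Day 365 and Day 281 antibody time points; if kept for the final analysis, earlier samples could count as 12- or 15-month values

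*SAP*

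**What the plan says.** For the secondary immunogenicity endpoints, SAP section 7.2 states that "Cohort 1 will be reported at Study Day 29, Study Day 57, Study Day 169 and Study Day 365/Early termination". For Cohort 2 the last time point is "Study Day 281 (15 Month FU)/Early Termination". Descriptive statistics are then produced by assessment time point.

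The schedules in Protocol Appendix 1 and SAP Appendix A give each final visit and early termination one shared column, which includes an immunogenicity sample. For vaccinated participants the SAP footnote reads "Participants that terminate early should complete all procedures for Study Day 365", and for those not vaccinated in this study "Participants that terminate early should complete all procedures for Study Day 281".

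On timing, SAP section 5.3.2 says: "For all immunogenicity data, the Study Day will be based on the nominal study day as captured in the CRF". SAP section 5.3.1 adds a selection rule: "If more than one assessment exists within a single visit window, the value closest to the protocol study visit will be used". That rule chooses between several values in one window. It does not say what happens to a value that lies outside every window.

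Protocol section 10.5.4 lists Day 365 as 12 months after the last dose for Cohort 1 and Day 281 as 15 months for Cohort 2, with no mention of early termination. Protocol Table 5 and SAP Table 1 also name Day 365 alone as the 12-month point for Cohort 1.

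On scope, the SAP introduction states: "This is a Statistical Analysis Plan for an Interim Analysis".

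**The concern.** The secondary objective is the long-term antibody response, so the last time point carries much of its message. A participant who leaves at, say, Day 100 is asked to give the sample belonging to the Day 365 or Day 281 column. If that visit is captured under the column's name, the nominal-day rule places a sample about three months after a Cohort 1 dose in the 12-month GMT, GMFR and seroconversion summaries. No rule in either document moves it, separates it or leaves it out.

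If titres fall after the peak, such a sample is higher than the same person's value at the nominal visit would have been, and persistence looks better than it is. The SAP's slot is also wider than the endpoint the protocol defines.

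**Working it through.** The plan states no figure for this point, so the check has three parts.

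**1. Does the text lead to one merged time point?**
- SAP 7.2 names the merged slot as a reporting time point.
- SAP 7.3 refers to an Appendix 9.1 for the immunogenicity time points. The SAP has no such appendix; its only schedule is Appendix A (10.1), where the final visit and early termination share a column.
- SAP 5.3.2 uses the nominal CRF day, not the sample date.
- SAP 7.3 censors only values after evidence of infection or after an off-study vaccine. Other early-termination samples remain.

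Merging is therefore the natural reading, although no sentence says in terms that early-termination values enter the Day 365 or Day 281 statistics.

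**2. How early could a sample be?** Gap g = nominal day − sample day.
- Against Day 365: Day 57 gives 365 − 57 = 308 days; Day 100 gives 265; Day 169 gives 196; Day 253 gives 112.
- Against Day 281: Day 85 gives 281 − 85 = 196 days; Day 100 gives 181; Day 197 gives 84.

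The final-visit window is +14 days in Protocol Appendix 1 and ±14 days in SAP Appendix A. The earliest in-window day is thus 365 or 351 for Cohort 1, and 281 or 267 for Cohort 2. Every sample day above lies outside both versions.

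**3. What could it do to the GMT?** The documents give no waning rate, exit day or early-termination rate. All three are assumptions here: titre half-life h = 60, 90 or 120 days; sample at Day 100; share f = 10% or 20% of the values in the slot.

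Ratio of an early value to the same person's later value: R = 2^(g/h). SAP 7.2 averages on the log scale, so GMT inflation = R^f = 2^(f·g/h). The GMFR is inflated by the same factor, because the baseline is unchanged.

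Cohort 1, g = 265:

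| h (days) | R | f = 10% | f = 20% |
|---|---|---|---|
| 60 | 21.4 | 1.36 | 1.84 |
| 90 | 7.7 | 1.23 | 1.50 |
| 120 | 4.6 | 1.17 | 1.36 |

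Cohort 2 under the same assumptions, g = 181: 2^(0.1 × 181/120) = 1.11 to 2^(0.2 × 181/60) = 1.52. For exit at Day 197 (g = 84), wider assumptions of h = 60 to 180 days and f = 5% to 30% give 2^(0.05 × 84/180) = 1.02 to 2^(0.3 × 84/60) = 1.34.

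Sub-cohorts are small. SAP 3.1 gives 106 participants if all enrol, and SAP 5.2 reports 15 groups (1a, five in 1b, nine in Cohort 2): 106/15 ≈ 7 on average, though sizes will differ. One early leaver among 7 in a Cohort 1 group gives f = 1/7, and R^f = 4.6^(1/7) = 1.24 to 21.4^(1/7) = 1.55. The assumed R of 4.6 to 21.4 also exceeds the 4-fold seroconversion threshold, so one early sample could change a participant's classification.

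Two limits apply. SAP 5.4 recodes titres below quantification to LLOQ/2, which caps R once late titres reach that floor; if both values sit there, R = 1. With no early-termination samples f = 0, and the factor is 1.00.

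**The case against.** The strongest reply is that this SAP pools nothing. It governs an interim with immunogenicity data to Day 57 for Cohort 1 and Day 29 for Cohort 2; its list of endpoints for this interim omits both merged slots. The SAP for the final analysis is not among the documents. A reader might infer from 7.2 that reported results already mix early and late samples; the documents do not support that. This part of the reply stands in full.

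Second, the slash in 7.2 may only repeat the schedule's column heading, and the CRF may label an early-termination visit as such. This stands as an uncertainty, because the CRF is not in the documents. It does not remove the gap: if the visit has its own label, the SAP still does not say how it is summarised.

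Third, a reader might infer that durability will be overstated. That goes too far:
- The protocol doses single-injection recipients who are seronegative at screening, but it does not say they were once positive. They may never have responded, so expected waning is not stated.
- A sample drawn before the peak could lower the value.
- Off-study vaccination was common (SAP 5.3.3), but nothing links it to early exit. Protocol 8.9.1 says that use of disallowed products does not require withdrawal, and the SAP follows such participants further.
- Participants lost to follow-up would give no exit sample, and those who withdraw consent are only encouraged to complete the exit procedures (Protocol 8.8).

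These points limit the number of affected samples and make the direction conditional. They do not show that the number is zero.

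**Conclusion.** The point holds in conditional form. The SAP states a merged reporting slot, assigns results by nominal day and has no rule for early-termination samples, whereas the protocol defines the endpoints as Day 365 and Day 281 alone. No interim result is affected. If the wording carries into the final analysis, uncensored samples taken months early would count as 12- or 15-month values where the CRF records them under the final visit, and can overstate persistence if titres wane after the peak.

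The size cannot be derived from the documents. Under the assumptions above, Cohort 1 inflation is about 17% to 36% at a 10% share and 36% to 84% at 20%. It is smaller in Cohort 2 and where titres reach the LLOQ/2 floor, and nil without such samples. The change should be made before the late data are summarised, because it is cheap and protects the long-term secondary endpoint.

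**What to change.** Amend SAP 7.2 and 5.3.2, and carry the text into the final SAP:

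1. Summarise Day 365 and Day 281 only from samples inside the scheduled visit window. First reconcile that window, which is +14 days in the protocol and ±14 in the SAP.
2. Assign each early-termination sample, by actual days since the last ARCT-021 dose, to the scheduled immunogenicity time point whose window contains it. For Cohort 2 this means expressing the windows on the same scale. If a regular sample already sits in that window, the closest-value rule in 5.3.1 decides.
3. If no window contains the sample, list it and leave it out of the time-point summaries.
4. Apply the same rule to T-cell results in the final SAP; they are outside this interim.

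The cost is a few lines of text and one derivation from sample dates. The n at the last time point becomes slightly smaller.

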2.5.2 Chemistry

2.5.2.1 Drug Substance mRNA-2002

The drug substance mRNA-2002 is an ~11.86 kilobase RNA that consists of 5' cap, a replicase gene encoding the VEEV non-structural proteins, and an RNA sequence encoding the SARS-CoV-2 spike glycoprotein. The general structure of mRNA-2002 is illustrated in [Figure 1](#).

[figure not shown]
[figure not shown]

Figure 1. mRNA-2002 Structure

The replicase gene encodes for 4 non-structural proteins (nsP1 to nsP4) from the Venezuela equine encephalitis virus (VEEV). The replicase is followed by an RNA sequence encoding the SARS-CoV-2 full length spike glycoprotein.

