10.5.5 Clinical Events of Special Interest Analyses

Statistical analyses of CESIs will be descriptive over timepoint in the safety and longitudinal safety populations. These endpoints include confirmed COVID-19 (including severe cases) and asymptomatic SARS-CoV-2 infection over timepoint and also analyzed as pooled and separately for the younger and older adult groups.

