5. GENERAL CONSIDERATIONS FOR DATA ANALYSIS

As there is no comparator group, there will be no formal hypothesis testing and therefore most of the statistical summaries will be descriptive and through displays of the data.

For this interim analysis, the following conventions will be used:

- Safety data:
 - All adverse event data reported for participants in Cohort 1a prior to Day 1 of study ARCT-021-02 are handled as medical history in the ARCT-021-02 study. The site was instructed to enter all medical history and ongoing adverse events from study ARCT-021-01 as medical history in this study.
 - All adverse event data reported for participants in Cohort 1b and Cohort 2 (all

subgroups) prior to Day 1 are handled as adverse events in the ARCT-021-02 study. For Cohort 1b, adverse event data occurring since end of study participation in ARCT-021-01 are summarized as adverse events but analyzed separately from those recorded in study ARCT-021-02 for the purpose of this analysis (since these participants received study vaccine in this study). For participants in Cohort 2, adverse event data occurring since end of study participation in ARCT-021-01 will be merged with AE data from Study ARCT-021-02 for the purposes of tabular presentation (since these participants do not receive additional study vaccine in this study)

- Immunogenicity data
 - Seroconversion will be defined as a 4-fold increase from baseline (Section 5.3.1) in antibody titer/concentration. An additional analysis at a threshold of 2-fold increase from baseline will also be performed.
 - Seropositivity at participant level for any timepoint (including baseline) is defined as a detectable level above LLOQ at that time point.

The summary statistics will consist of absolute and relative frequencies (percentages) for categorical variables and mean, median, standard deviation, minimum, maximum as well as number of non-missing observations will be used for discrete and continuous variables. For titers, geometric mean and 95% confidence intervals (CIs) will also be provided, as well as the percent geometric coefficient of variation (%GCV).

Summary statistics will also be provided for change from baseline using mean, median, standard deviation, minimum and maximum as well as the number of non-missing observations. Where applicable, the percentage change from baseline will be provided. For titer, geometric mean fold rise and 95% CIs will also be provided, as well as the %GCV.

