7.3 Immunogenicity Endpoint Summaries

Participants with evidence of SARS-CoV-2 infection or that received an off-study vaccine will be censored from the immunogenicity analysis for all timepoints and evaluations beyond earlier of the time point at which evidence of SARS-CoV-2 infection occurred or the time point at which off-study vaccine was received. Evidence of SARS-CoV-2 infection includes a positive PCR test or a positive antinucleocapsid antibody test (defined as a concentration $\geq 5,000$ AU/ml)

The timepoints for analysis of each of the immunogenicity parameters is shown in Appendix 9.1.

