7.3.1.1 Binding Antibodies

Endpoint titers of Binding antibodies, by participant, and time point, will be listed for each of the 3 tests listed below. Mean titer, GMC, GMFR, 95% CIs, median, minimum, and maximum values and number and percent of participants seroconverting will also be summarized by cohort/sub-cohort and time point for:

- Anti-spike glycoprotein
- Anti-RBD
- Nucleocapsid

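### Anti-nucleocapsid antibody, an infection marker in this trial, is summarised as a vaccine response, and its seroconversion rule is not tied to the infection rule that censors the other antibody results

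*SAP*

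**What the plan says.** **Anti-N as a response.** SAP 7.2 item 1 places N-antigen in the secondary endpoint, with mean, GMC and GMFR for "IgG antibodies against the full-length SARS-CoV-2 recombinant spike protein antigen, RBD and N-antigen at multiple time points in each cohort". The assay list in the same section repeats it under binding antibody responses: "Total IgG against the full-length SARS-CoV-2 recombinant spike protein, RBD and N-antigen will be assessed using a Meso-Scale Discovery (MSD) multiplex technology". SAP 7.3.1.1 goes further, stating that "number and percent of participants seroconverting will also be summarized by cohort/sub-cohort and time point for" three tests, of which the third is nucleocapsid.

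**Where N is absent.** SAP 7.2 item 2 limits the seroconversion endpoint to neutralising antibody and to "IgG antibodies against the full-length SARS-CoV-2 recombinant spike protein antigen and spike protein RBD will be assessed at the above mentioned time points". SAP 2.2.2 names only spike and RBD as binding antigens, and protocol 1.2.2 only spike and its subunits. On the vaccine, protocol 2.5.2.1 states: "The replicase is followed by an RNA sequence encoding the SARS-CoV-2 full length spike glycoprotein".

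**Anti-N as an infection marker.** Protocol 9.3.7 counts a positive anti-N test, in a participant who was negative before entry, as asymptomatic infection, which is a Clinical Event of Special Interest (CESI). Both analyte lists place anti-N under SARS-CoV-2 confirmation.

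**The two rules.** SAP 5: "Seroconversion will be defined as a 4-fold increase from baseline (Section 5.3.1) in antibody titer/concentration", with a further analysis at 2-fold. SAP 7.3: "Evidence of SARS-CoV-2 infection includes a positive PCR test or a positive antinucleocapsid antibody test", with positive anti-N set at 5,000 AU/ml or more. Immunogenicity results are censored for time points *beyond* the one with that evidence.

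**CESI reporting.** Protocol 10.5.5: "Statistical analyses of CESIs will be descriptive over timepoint in the safety and longitudinal safety populations", pooled and by age group. SAP 8.1.8 provides listings and narratives only.

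**The concern.** A vaccine whose only SARS-CoV-2 antigen is spike gives no reason to expect an anti-N response. An anti-N GMFR or seroconversion percentage therefore says nothing about the vaccine. Set beside spike and RBD under the same column labels, it can be misread as vaccine response. This interim supports a regulatory filing (SAP 4), so the labelling matters.

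The more substantive issue is bias in the spike, RBD and neutralising summaries. These are meant to exclude results affected by infection. PCR testing is prompted by symptoms or exposure (protocol 6.2.4), so an unrecognised infection without symptoms is found mainly through anti-N. If the anti-N rule misses it, or finds it but leaves in the result from that visit, an infection-boosted value enters a geometric mean that is described as following vaccination.

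**Working it through.** The documents give no figure to reproduce: the 5,000 AU/ml cut-off has no derivation, no LLOQ is stated for the N assay, and there is no sample size calculation.

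**Step 1. Fold rule against cut-off.** A k-fold rise from baseline B stays below the cut-off when k × B < 5,000, that is, when B < 5,000/k.

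- k = 4: B < 5,000/4 = 1,250 AU/ml
- k = 2: B < 5,000/2 = 2,500 AU/ml

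Rises from 100 to 400 and from 1,000 to 4,000 are both N seroconversion and both below the cut-off. From a baseline of 100, a rise of 5,000/100 = 50-fold is needed to count as infection. Without a positive PCR, such a participant is an N seroconverter in SAP 7.3.1.1 and uninfected everywhere else.

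**Step 2. The detection visit.** SAP 4.4 and 7.2 give the ARCT-021-02 visits available at this interim: Day 29 for Cohort 2, and Days 1, 29 and 57 for Cohort 1. If censoring begins after the visit with evidence:

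- Cohort 2, anti-N first at 5,000 or more on Day 29: no ARCT-021-02 result is removed.
- Cohort 1, first on Day 57: nothing is removed.
- Cohort 1, first on Day 29: only Day 57 is removed.

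This needs no fold rise, so it can arise in every sub-cohort.

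**Step 3. Where a fold rise can be calculated.** SAP 5.3.1 sets baseline at ARCT-021-02 Day 1 for Cohort 1 and at Parent Study Day 1 for Cohort 2. Assuming that anti-N follows the availability shown in SAP Table 2, Cohort 1 has a baseline throughout. Cohorts 2(A), 2(B) and 2(C) have none, so the conflict in Step 1 cannot arise there. For 2(F) and 2(H), Table 2 marks Parent Study Day 1 as available, but the text of SAP 4.4 does not name these cohorts among those with Parent Study data; this should be settled.

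**Step 4. Possible size.** The GMC is the antilog of the mean log value. If one of n values is multiplied by f, the mean log rises by log(f)/n, and the GMC is multiplied by f^(1/n). The same holds for the GMFR if the baseline is unaffected. Neither f nor n is in the documents. For scale only, SAP 3.1 gives 106 participants if all enrol, and SAP 5.2 defines 15 sub-cohorts (1a, five in 1b, nine in 2), so 106/15 is about 7.

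| n (assumed) | f = 5 | f = 10 | f = 20 |
|---|---|---|---|
| 5 | 1.38 | 1.58 | 1.82 |
| 7 | 1.26 | 1.39 | 1.53 |
| 10 | 1.17 | 1.26 | 1.35 |
| 20 | 1.08 | 1.12 | 1.16 |

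One such participant can also add up to 100/n percentage points to a seroconversion rate: 10 points at n=10 and 5 at n=20.

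**The case against.** A reader might infer that infection-boosted spike results do stay in the analysis. The documents do not show that. It takes a true infection, no positive PCR, and either anti-N that stays below 5,000 AU/ml or the literal reading of the censoring sentence. SAP 7.3 already censors on PCR and on anti-N, and it says that evidence *includes* these, which leaves some room.

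A reader might also infer that every 4-fold anti-N rise is an infection. That is not supported either. SAP 5.4 recodes antibody titers below quantification to LLOQ/2. If this covers binding concentrations, a change from unquantifiable to only 2 × LLOQ scores as 4-fold. With no LLOQ or assay variability given, a small rise may be noise. The 4-fold rule is no better validated as an infection criterion than 5,000 AU/ml, so it should not replace it.

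The defence can add that the seroconversion endpoint proper, in SAP 7.2 item 2, excludes N; that immunogenicity is secondary and descriptive, so no error rate is affected; and that an interim limited to primary and secondary objectives (SAP 2) need not carry the full CESI analysis, since SAP 8.1.8 lists every case.

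All of this stands, and it limits the size of the point. It does not explain why a marker of infection is tabulated as a response, nor does it connect the two rules or settle the detection visit.

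**Conclusion.** The point holds in a limited form. It is certain from the text that anti-N is summarised among the vaccine responses, against SAP 2.2.2, SAP 7.2 item 2 and the protocol's own use of the marker. It is also certain that a 4-fold anti-N rise from a baseline below 1,250 AU/ml can fall short of the censoring rule, and that the wording of SAP 7.3 may leave in the result at the detection visit, which for Cohort 2 is the only ARCT-021-02 visit at this interim.

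That any participant is affected is not established. The factors in the table rest on assumed boosts and sub-cohort sizes and are not estimates of bias in this trial. The missing CESI table is a secondary matter at the interim. Because the repair is cheap and the sub-cohorts are likely to be small, the change is worth making.

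**What to change.** 1. **SAP 7.2 and 7.3.1.1:** remove anti-N from the response and seroconversion summaries. Report it, uncensored, as an infection marker. Correct SAP 4.3, which labels nucleocapsid as a spike protein antigen.
2. **SAP 7.3:** keep 5,000 AU/ml as the primary rule, but state that results at the detection visit are themselves excluded. Add a sensitivity repeat of the spike, RBD and neutralising summaries that also excludes results from a 4-fold or greater anti-N rise onward. Limit it to participants with an anti-N baseline, and note that rises from LLOQ/2 may be noise.
3. **CESIs:** at the latest in the final analysis, tabulate them over time, pooled and by age group as protocol 10.5.5 states, including asymptomatic infection detected by serology.

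The cost is revised wording, one repeated immunogenicity summary and, by the final analysis, the CESI table that the protocol already calls for. A few uninfected participants may be dropped in the sensitivity analysis. SAP 5.1 bars changes once the interim data have been pulled; if that has happened, the changes belong in the SAP for the final analysis.
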